8.6 Delivery of BRCA test result

The BRCA-DIRECT system will alert participants when their test result is ready. They will either receive their result digitally or via a telephone consultation with a genetic counsellor.

It is anticipated that 94-95% of the study cohort will have a negative (normal) result and 5-6% will have a positive result indicating the presence of a pathogenic_variant or a VUS.

- All participants with a positive result will receive their results via telephone consultation with a genetic counsellor (**estimate 5-6% of total cohort**)
- The majority of participants with a negative result indicating normal genes will receive their result digitally (**97.5% of total cohort**)
- An additional randomly selected 2.5% of participants with a negative result will receive their results via telephone consultation with a genetic counsellor (**2.5% of total cohort**)

8.6.1 Digital receipt of result (participants with no pathogenic_variant detected)

The participant will receive a message informing that their test results are available. The message will contain a link to digital notification of their negative (normal) result. A results letter and copy of the molecular genetics laboratory report will be sent to the participant via secure email/post.

8.6.2 Receipt of result via telephone consultation with a genetic counsellor (all participants with pathogenic_variant plus 2.5% with a normal result)

The participant will receive a message informing that their test results are available. The message will contain a link to the study digital calendar to book an appointment with a genetic counsellor. Following the appointment, a results letter and copy of the pathology report will be sent to the participant via secure email/post.

If a participant does not book a genetic counselling appointment, an SMS/email reminder will be sent 3,4 and 5 days after notification that test results are available.

8.7 Post-test result anxiety assessment

Seven days after notification that their test results are available, participants will be asked to complete digitally:

- STAI Y-1 anxiety questionnaire

If this questionnaire is not completed, an SMS/email reminder to complete it will be sent to the participant 10, 11 and 12 days after notification that test results are available.

8.8 Participant user feedback

Seven days after receiving their test results, participants will be invited to complete a digital user feedback survey exploring user experience of the BRCA-DIRECT platform and acceptability of the method for providing information about genetic testing and results.

During the internal pilot phase participants will also have the opportunity to register for an optional telephone interview with a BRCA-DIRECT researcher to explore their experience of participating in the study in more detail, to highlight any unanticipated logistical problems that require resolution. This will be capped at 50 participants.

Following the pilot phase participants will have the opportunity to register interest for an optional video (or telephone if required) interview with a BRCA-DIRECT researcher. The interviews will expand on data from the pilot phase interviews and will explore the participant's motivations for, and experiences of, BRCA-testing via the BRCA-DIRECT digital platform at an early stage in their breast cancer diagnosis and treatment. Information will inform future adaptations or considerations for implementation of the pathway more broadly.

We will be conducting interviews in participants who are newly diagnosed, pre-surgical at time of enrolment to the study AND randomised to the digital pre-test information arm. We aim to complete interviews with all eligible participants who register their interest OR a minimum of 50 eligible participants, whichever is lower. No retrospective invitations to participate will be sent to participants who have already completed their involvement in BRCA-DIRECT.

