8.9 Final anxiety assessment

Twenty eight days after receiving their test results, participants will be asked to complete digitally:

- STAI Y-1 anxiety questionnaire
- Knowledge questionnaire

If this questionnaire is not completed, an SMS/email reminder to complete it will be sent to the participant 31, 32 and 33 days after notification that test results are available.

Participants will also be offered a second opportunity to provide user feedback if this was not done previously.

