8.9.1 Schedule of patient reported outcome assessments

| Time point | STAI Trait (Y-2) | STAI State (Y-1) | Intolerance of Uncertainty | Knowledge Score | Participant Satisfaction Survey (+ optional telephone interview) |
|---|------------------|------------------|----------------------------|-----------------|--|
| T0 - Baseline | ✓ | ✓ | ✓ | ✓ | |
| T1 – 24 hours after giving consent for genetic test to proceed | | ✓ | | ✓ | |
| T2 – 7 days after notification that test results are available | | ✓ | | | ✓ |
| T3 – 28 days after notification that test results are available | | ✓ | | ✓ | ✓ (reminder if not done at T2) |

All calls to the telephone hotline will be logged on BRCA-DIRECT system by the genetic counsellor who took the call (content and duration of call).

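### Post-pilot researcher interviews are offered only to a subset of digital-arm women, and nothing stops them taking place before the day-28 STAI and knowledge questionnaires

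*Combined protocol and SAP*

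**What the plan says.** **Who is interviewed.** In the internal pilot, section 8.8 offers a telephone interview, capped at 50, with no restriction by arm. After the pilot, the interviews are limited to the digital arm, and within it by stage of treatment: "We will be conducting interviews in participants who are newly diagnosed, pre-surgical at time of enrolment to the study AND randomised to the digital pre-test". Taking part is voluntary: women have the "opportunity to register interest for an optional video (or telephone if required) interview with a BRCA-DIRECT researcher". The target is "all eligible participants who register their interest OR a minimum of 50 eligible participants, whichever is lower", which works as a ceiling of about 50 despite the word for a minimum.

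**What is discussed.** The interviews "will explore the participant's motivations for, and experiences of, BRCA-testing via the BRCA-DIRECT digital platform". They are not described as counselling or as giving genetic information.

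**When.** Section 8.8 places the interviews under user feedback, which opens seven days after results. The schedule in 8.9.1 puts the optional interview in the column headed "Participant Satisfaction Survey (+ optional telephone interview"), ticked at T2 (day 7) with a reminder at T3. Section 8.8 also rules out inviting women whose participation is already complete. No section dates the interview itself.

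**What follows.** Section 8.9 sets the final questionnaires: "Twenty eight days after receiving their test results, participants will be asked to complete digitally" the STAI Y-1 and the knowledge questionnaire, with reminders up to day 33. The power table in 12.1 gives STAI state at T3 its own row and a margin of 3. Section 12.4 does not mention the interviews.

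**The concern.** A contact offered to one arm after allocation cannot be balanced by randomisation. Here it is a live conversation with a researcher about the woman's own BRCA testing. It is not one of the steps that section 1.8 lists for the pathway under test, and it can fall between two outcome measurements. If it changes state anxiety, the T3 comparison partly reflects the interview and not the way pre-test information was delivered. A fall in anxiety would make non-inferiority easier to declare; a rise would make it harder. What is at stake is one secondary comparison with a stated margin, STAI at T3.

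**Working it through.** **1. The plan's own figures (section 12.1).** Inputs: SD 13.5, margin 3, one-sided 0.025, 1:1 allocation, 800 women at T3 after 20% attrition.

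- n per arm for 80% power = (1.960 + 0.842)² × 2 × 13.5² / 3² = 317.9, so 318 per arm or 636 in total. The plan states 636.
- With 400 per arm, SE = 13.5 × √(2/400) = 0.955. Power = Φ(3/0.955 − 1.960) = 88.2%. The plan states 85-90%.

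Both reproduce.

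**2. Share of the arm exposed.** The ceiling in 8.8 is 50 women, and the digital arm at T3 is 500 × 0.8 = 400. The share is at most 50/400 = 12.5%. With 25 interviews (assumption) it is 6.25%.

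**3. Shift in the arm mean.** Shift = share × change per interviewed woman. The documents give no such change; 2 to 5 STAI points is an assumption, and so is its sign. The table also assumes that every interview precedes T3 and that every interviewed woman completes T3.

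- Error at the margin, if the shift favours digital: Φ(shift/0.955 − 1.960).
- Power, if the shift goes against digital: Φ((3 − shift)/0.955 − 1.960).

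| Interviewed before T3 | Assumed change per woman | Shift in arm mean | Share of margin | Error at margin if it favours digital (nominal 2.5%) | Power if it goes against digital (88.2% with no shift) |
|---|---|---|---|---|---|
| 50 | 2 | 0.25 | 8% | 4.5% | 82% |
| 50 | 5 | 0.63 | 21% | 9.6% | 70% |
| 25 | 2 | 0.13 | 4% | 3.4% | 85% |
| 25 | 5 | 0.31 | 10% | 5.1% | 80% |

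For the interviews alone to move the arm mean by the whole margin, each of 50 women would have to change by 3/0.125 = 24 points.

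**4. Under the model as worded.** Section 12.4 lists fixed effects for baseline, arm, centre and time point, with no arm-by-time term. The arm effect is then averaged over T1, T2 and T3. With equal weights (assumption), a T3-only shift of 0.25 to 0.63 becomes about 0.08 to 0.21, or 3-7% of the margin. With an assumed within-woman correlation of 0.6 and 400 per arm:

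- SE = 13.5 × √[((1 + 2 × 0.6)/3) × (2/400)] = 0.817.
- Error at the margin = 3.2% to 4.4%.

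**5. Other outcomes.**

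- Uptake and the T1 scores are fixed before results are returned, so before any interview.
- T2 STAI is requested at the same day-7 point at which feedback opens.
- T3 knowledge has no stated margin. Borrowing the T1 margin of 1.40, each of 50 women would need to change by 1.40/0.125 = 11.2 points on a 12-point test.

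**The case against.** The strongest reply is that a possibility is being treated as a flaw. Section 8.8 sets no interview date, so some or all interviews may follow T3. The schedule's column refers to a telephone interview, which is the pilot format, so it is weak evidence of when the post-pilot video interviews happen. This stands as far as it goes: contact before T3 is permitted, not certain.

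A reader might infer that the whole digital arm receives an extra consultation. It does not: the interview is optional and limited to newly diagnosed, pre-surgical women, about 50 at most.

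A reader might also infer that the interview supplies the human contact that the digital arm was meant to do without. The documents do not support that. Digital-arm women can call a genetic counsellor on the hotline (5.1, 8.3), and women in either arm with a pathogenic variant or VUS get their result by telephone (5.2). The difference is that the hotline belongs to the tested pathway and its use is an outcome, whereas the research interview is neither.

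Nor do the documents show that the interview lowers anxiety or teaches anything. Bias towards non-inferiority is one possibility of two, and an effect on knowledge is conjecture.

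Finally, section 12 says the study is not primarily powered for these measures. That limits the importance of the point but does not answer it, because 12.1 still sets a margin and a power for STAI at T3.

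**Conclusion.** The point holds as a gap in timing. After the pilot, only digital-arm women can be interviewed, and the plan lets this happen before the T3 questionnaires. The exposure is confined to T3, chiefly STAI, and reaches at most 12.5% of the digital arm.

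The error and power figures are upper-end illustrations. They need all 50 interviews to precede T3, complete T3 data in those women, a uniform assumed change and a stand-alone T3 comparison. They roughly halve or better with 25 women, measured as the departure from 2.5% or from 88.2%, and they shrink under the averaged model.

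This does not threaten the primary conclusion on uptake. It is worth correcting because the correction is cheap and removes a one-arm difference that no analysis can cleanly undo.

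**What to change.** In section 8.8, keep invitation and registration at T2, which respects the rule against retrospective invitations. Open booking of post-pilot interviews only when the platform has recorded the T3 STAI and knowledge questionnaires as submitted, or when the last T3 reminder (day 33) has lapsed. Record the date of every interview. Reword the target so that it is clear whether 50 is a ceiling or a minimum.

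For interviews already held before T3, report how many there were. Any analysis that leaves out those women's T3 scores should be labelled exploratory, because it removes self-selected, newly diagnosed women from one arm only and cannot separate the interview's effect from selection.

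The cost is a sentence of protocol text, a booking trigger on a platform that already manages calendars and action-linked messages (section 13), and interviews about three weeks later with slightly less fresh recall. No sample size or power figure changes.

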8.9 Final anxiety assessment

Twenty eight days after receiving their test results, participants will be asked to complete digitally:

- STAI Y-1 anxiety questionnaire
- Knowledge questionnaire

If this questionnaire is not completed, an SMS/email reminder to complete it will be sent to the participant 31, 32 and 33 days after notification that test results are available.

Participants will also be offered a second opportunity to provide user feedback if this was not done previously.

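### T3 and the T2 satisfaction survey have conflicting start points, and the T2 STAI, timed from notification, can come before a telephone result

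*Combined protocol and SAP*

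**What the plan says.** **T2.** Section 8.7 asks for the STAI state form "Seven days after notification that their test results are available", and the schedule in 8.9.1 agrees: "7 days after notification that test results are available". The satisfaction survey sits on the same T2 row of that schedule, but section 8.8 invites women to it "Seven days after receiving their test results".

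**T3.** Section 8.9 sets the STAI and knowledge questionnaire "Twenty eight days after receiving their test results". Section 10 also counts the final STAI from receipt when it defines the end of the study. The schedule in 8.9.1 has "28 days after notification that test results are available", and the reminders in 8.9 are counted from notification.

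**Result delivery.** Sections 5.2 and 8.6 give every positive result (pathogenic variant or VUS) by telephone, together with a randomly selected 2.5% of negatives. Under 8.6.2 the message to these women carries a calendar link for booking a consultation. If no booking is made, "an SMS/email reminder will be sent 3,4 and 5 days after notification that test results are available". No latest date for the call is stated. Digital recipients get a message with a link that they must open to see the result (8.6.1).

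**The concern.** Notification and receipt are treated as if they were one event. For a telephone result they are two events separated by a booking step, and for a digital result they are separated by however long the woman takes to open the link.

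This produces two linked but distinct faults. First, the T3 assessments and the T2 survey cannot be programmed consistently from the text, because different sections start the clock on different days. Second, the T2 STAI has a single clear anchor, but that anchor does not guarantee that the result has been heard. Section 8.7 is headed as a post-test result assessment, and anxiety following test results is a stated secondary objective (2.3). In women waiting for a counsellor's call, T2 may record anticipation and not a reaction to the result. T3 is three weeks later and cannot recover the early response.

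**Working it through.** **1. Start points side by side**

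| Item | Section | Clock starts at |
|---|---|---|
| T2 STAI | 8.7 and 8.9.1 | notification in both |
| T2 STAI reminders (days 10, 11, 12) | 8.7 | notification |
| T2 satisfaction survey | 8.8 | receipt |
| T2 satisfaction survey | 8.9.1 | notification |
| T3 STAI and knowledge | 8.9 | receipt |
| T3 STAI | 10 | receipt |
| T3 reminders (days 31, 32, 33) | 8.9 | notification |
| T3 STAI and knowledge | 8.9.1 | notification |

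For the STAI, the direct conflict is at T3. At T2 only the survey conflicts.

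**2. Effect within section 8.9.** Let the result be received r days after notification. The invitation is due on day 28 + r after notification, while the reminders stay on days 31, 32 and 33.

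- r = 3: day 31, the same day as the first reminder.
- r = 4: day 32, one day after the first reminder.
- r = 6: day 34, after all three reminders.

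From r = 4 onward, at least one reminder comes before the invitation.

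**3. Can the T2 STAI precede the result?** Booking reminders run to day 5 and the STAI goes out on day 7. Section 8.3 asks for pre-test calls to be booked within three working days if possible; nothing similar is stated for result calls. If the same wait is assumed for illustration, a woman who books on day 5 could have her call on day 5 + 3 = day 8 or later. No section holds the questionnaire until the call is logged. The general pathway-management requirement in section 13 states no such rule.

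**4. Size of the telephone group.** Inputs: positive share p = 5% to 6% and 2.5% of negatives by telephone (5.2, 8.6); uptake 90% of 1000 = 900 tested (12.1).

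Share by telephone = p + 0.025 × (1 − p)

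- p = 5%: 0.05 + 0.025 × 0.95 = 0.0738; × 900 = 66 women.
- p = 6%: 0.06 + 0.025 × 0.94 = 0.0835; × 900 = 75 women.

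The 900 here is the number tested under the uptake assumption. It coincides with the 900 that the power table gives for STAI at T2 after 10% attrition, but it is a different quantity.

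**5. Effect on the between-arm comparison.** The plan's figure reproduces: margin 3, SD 13.5, one-sided 0.025 and 80% power give 318 per arm, or 636 in total. Power is 91.5% with 900 and 88.2% with 800, inside the stated ranges. Timing does not enter these figures.

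For bias, take two assumed values that are not in the documents: a 10-point shift in STAI when it is completed before the result, and a 20-percentage-point difference between arms in how often that happens among telephone recipients. The bias is then 0.0738 × 0.20 × 10 = 0.15 to 0.0835 × 0.20 × 10 = 0.17 points, against a margin of 3.

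**The case against.** The strongest reply is that the T2 STAI has one consistent anchor, so its timing is a design choice and not an error, and that the wording conflict at T3 is harmless for interpretation because a call would have to be delayed beyond 28 days to follow the questionnaire. Much of this stands. A reader might infer that the mixed wording is what lets women complete the T2 STAI early. The documents do not support that: the risk comes from choosing notification as the anchor, and it would remain if every section used that word.

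A reader might also take 66 to 75 as the number affected. It counts everyone told by telephone. The documents give no appointment waiting time, and some women sent the STAI on day 7 will complete it later, after their call. The affected number could be close to zero.

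Nor is there a case that the randomised comparison is compromised. Telephone delivery depends on the test result and a separate random selection, not on the pre-test arm, so early completion should be roughly balanced.

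Finally, consultations are recorded (15.1) and participants' progress is mapped by login (15.3), so early STAIs could probably be identified at analysis. That helps, but the plan does not say this will be done, and it does not resolve the conflict over when T3 is due.

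**Conclusion.** Both faults hold. The start points for T3 and for the T2 survey contradict each other and must be reconciled. The T2 STAI is consistently timed, but from an event that for telephone recipients is not the result.

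Telephone results reach about 7.4% to 8.4% of tested women, or 66 to 75 if 90% of 1000 are tested. This is a ceiling for that route and includes every woman with a pathogenic variant or VUS. Digital recipients who open the link late would be additional, and they cannot be counted from the documents. The share who complete T2 before hearing their result cannot be computed.

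Between-arm bias is probably small, and the sample-size figures are unaffected. The main harm is to what T2 means as post-result anxiety in women with positive results. The point merits correction but does not threaten the primary outcome.

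**What to change.** Use one start point in 8.7, 8.8, 8.9, 8.9.1 and section 10, for invitations and reminders alike: the logged date of receipt, meaning the result link opened or the telephone consultation recorded as completed. State a fallback prompt, counted from notification, for women with no logged receipt, so that they are not lost from T2 and T3.

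Do not exclude STAIs dated before receipt. That would be a post-randomisation exclusion driven by participants' behaviour, and among telephone recipients it would fall mostly on women with positive results. Flag them, and report T2 with and without them as a sensitivity analysis.

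The cost is small. The platform already releases the BRCA-test consent form only after a logged consultation or page visit (8.3, 16.2), so the same kind of trigger can be applied here. T2 and T3 will fall a few days later for telephone recipients and for digital recipients who open the link late.

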8.9.1 Schedule of patient reported outcome assessments

| Time point | STAI Trait (Y-2) | STAI State (Y-1) | Intolerance of Uncertainty | Knowledge Score | Participant Satisfaction Survey (+ optional telephone interview) |
|---|------------------|------------------|----------------------------|-----------------|--|
| T0 - Baseline | ✓ | ✓ | ✓ | ✓ | |
| T1 – 24 hours after giving consent for genetic test to proceed | | ✓ | | ✓ | |
| T2 – 7 days after notification that test results are available | | ✓ | | | ✓ |
| T3 – 28 days after notification that test results are available | | ✓ | | ✓ | ✓ (reminder if not done at T2) |

All calls to the telephone hotline will be logged on BRCA-DIRECT system by the genetic counsellor who took the call (content and duration of call).

8.10 Additional notification of test results to the participant's health care team

For each participant, a copy of the genetic test results will also be sent securely to:

- The participant's oncology consultant and breast care nurse
- The local site molecular diagnostic laboratory
- The local clinical genetics service
- The participant's GP

Regular summaries of results and those in whom testing is underway will be sent securely to the breast MDT coordinators at a frequency according to local site preference.

8.11 Clinical Genetics referral

For all individuals in whom a BRCA1/BRCA2/ PALB2 pathogenic_variant is detected, clinical genetics referral will be advised on the report and patient letter. The results will also be sent to clinical genetics so they can ensure all positive participants are referred.

[figure not shown]
For all individuals with a significant family history of breast/ovarian cancer in whom no BRCA pathogenic_variant was detected, additional detailed evaluation of family history will be advised on the report and in an individualised standard patient letter.

8.12 Participant withdrawal

[figure not shown]
Participants may withdraw from the study at any time, if they so wish, without giving a reason. Information about withdrawal is included in the patient information leaflet, as well as on the BRCA-DIRECT platform. Participants can withdraw by contacting their clinical team, the study hotline or emailing [contact].

No further data will be collected about that individual. Study data collected up to that point will be retained for audit purposes. Samples derivatives (DNA) and data generated within the NHS diagnostic environment will be retained.

